1 BACKGROUND AND PROJECT RATIONALE

One of the important factors to cause serious health impacts among children is lack of access to clean water (Darvesh et al., 2017). Various types of pathogens can affect children in many different ways likewise the ones causing water-borne diseases such as cholera, diarrhea and intestinal parasitic infections (Bethony et al., 2006). There are various causes of fecal contamination of drinking water (Wright et al., 2004a). Even if the water at the source and at the point-of collection is safe, unhygienic conditions during transport and storage can lead to recontamination (Wright et al., 2004b). Dirty hands, storage containers used for water handling may contaminate water during collection, transportation and storage (Rufener et al., 2010). As a result, it has been estimated that 1.7 million children face death each year due to unsafe water and poor hygiene condition, where diarrhea is the primary cause of death in 9 out of 10 children whereas one third out of 1.7 million deaths occur in South East Asia (Khayet et al., 2003). Yet, to reduce these water-borne diseases, improving the water quality in the households and safe storage have shown to be effective (Fewtrell and Colford, 2004). Furthermore, there are different methods to reduce water-borne diseases (e.g. diarrhea, intestinal parasitic infections) morbidity and mortality and all of them may require behavioral change (Ashbolt, 2004; Bethony et al., 2006)

Moreover, adequate nutrition is also essential among children for ensuring healthy growth, proper organ formation and function, strong immune system, and neurological and cognitive development (De Onis et al., 2012). However, nutrition as a cross cutting theme, is closely interlinked with multifactorial determinants. The immediate causes of malnutrition in children is insufficient nutrient intake and food insecurity, while the underlying contributing factors include lack of access to safe water and sanitation, recurrent infectious diseases, lack of awareness on health and hygiene where the results indicated that both must be improved in conjugation to have an effect (Black et al., 2008). Therefore, it is of utmost importance to understand whether the contribution of water, sanitation and hygiene (WASH) interventions to minimize malnutrition (low BMI, inadequate dietary diversity, low hemoglobin (Hb) level) and decrease in incidence of infectious diseases such as intestinal parasitic infections among children.

Nepal faces a plethora of problems related to drinking water (Prüss-Ustün et al., 2014). In 2015, the WHO/UNICEF JMP reported that 92% of the Nepalese population had access to improved water, and hence, met the specific MDG target (WHO/UNICEF, 2015). However, about 71% of the water sources are contaminated with fecal coliforms. In addition, in 82 percent of households with access to an improved source, water is fecally contaminated. The proportion of households without improved drinking water using appropriate treatment methods is 14 percent (GON and UNICEF, 2015). According to the data from the Department of Health Service (DHS), Nepal, about 3500 children die each year due to water-borne diseases (Aryal et al., 2012). Intestinal parasitic infections and diarrheal diseases due to inadequate water and hygiene are the principal causes (Sah et al., 2013). Although, Nepal has abundant water resources, competing uses and often poor water resource management compromise quantity, quality and access (Dixit et al., 2012).

Similarly, malnutrition is the major underlying cause of child mortality within the country where 36% are stunted, 10% wasted and 27% are underweight. Anemia among the infants and children is high i.e. 53% (DHS, 2016). Complementary foods are not introduced in a timely fashion for all children and only one fourth of the age 6-23 months are fed appropriately based on recommended infant and young child feeding practices (DHS, 2016). Apart from taking insufficient intake of safe and quality food, the consumption of unbalanced food is also a problem, which together is responsible for the chronic nutritional problem in children.

As WASH and health, including nutritional status, are closely interlinked with multiple determinants, the objective of this study is to assess if improved water quality at the point of

consumption together with improved hygiene and sanitation conditions reduces the health burden (intestinal parasitic infections, anemia, malnutrition, nutritional deficiency) of children living in rural households in Nepal.

Previous collaboration activities with Helvetas in the WARM-P project area revealed significant changes in the hygiene and sanitation condition after a WASH education campaign. Nevertheless, a significant degree of water recontamination between the point of collection and the point of consumption was observed. The proposed study aims at assessing the impact of such an effective training strategy at household level, if the training is combined with an improved water quality intervention.

The impact study will be implemented in Western Nepal in collaboration with Helvetas International Cooperation in the context of their activities on Water Safety Planning in water supply schemes. The evaluation will assess the impact of two interventions aiming at increasing water quality at the point of consumption.

The study is an observational study. Children's caretakers in participating households, will participate twice in a quantitative interview. Health data will be collected from one or two children of participating households. Children's health will be analyzed on the basis of the following indicators: diarrhoea incidence (questionnaire), parasite infection (collection and analysis of stool samples), anthropometric measurements, clinical examination and finger prick tests. The examination of children will be conducted by qualified and trained health personnel. Only households will be involved in the study that have provided written informed consent.

The process of data collection will not cause any health risks to participating humans and therefore can be categorized into Risk category A in accordance with HRO Art.7.

Participating households will not receive any direct compensation for participating in the survey. However, participants will be informed about the outcomes of the study and the results of their personal examination. Those found infected with parasites will be treated in accordance with their infection at recommended doses following standard treatment schemes of WHO.

The study will contribute to understanding the effect of WASH interventions for achieving an improved health status of the targeted population. It will estimate the magnitude of the problems related to contaminated drinking water and critical hygiene in the study areas where the interventions will be carried out in comparison to control area. An evidence-based program for preventing WASH related diseases will be evaluated that can be replicated in other countries similar to Nepal. It is expected that insights gained from this study will improve future National programs and policies related to water supply, drinking water quality, hygiene and health in Nepal.

2 PROJECT OBJECTIVES AND DESIGN

2.1 Hypothesis and primary objective

Hypothesis

The main assumption is based on the idea that improved water management leading to safe water at the point of consumption either through system level chlorination or adequate household water treatment at the point of consumption and hygiene infrastructure such as hand washing infrastructure and improved sanitation will lead to a reduction of the water-borne diseases including intestinal parasitic infections.

Goal

The impact of a water quality intervention that comprises of system level water chlorination versus an intervention that comprises adequate household water treatment (including an effective filter and improved filter handling practice) as well as the impact of improved infrastructure for handwashing and sanitation together with hygiene education are evaluated.

2.2 Primary and secondary endpoints

Specific objectives

- 1) To analyze the impact of a water quality and hygiene intervention on:
- Water quality at the point of collection as well as at the point of consumption;
- Availability, condition and use of water, sanitation and hygiene infrastructure; and
- Knowledge, attitude and practice (KAP) of water management, sense of ownership, and hygiene.
- 2) To determine the burden of water-borne diseases (diarrhea and intestinal parasitic infections), malnutrition, nutritional deficiency and anemia among children within the households before and after the intervention.

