implemented. The proposed study suggests to assess the improvement of water supply together with strategies to assure drinking water safety and the construction of handwashing stations and latrines. This infrastructural component will be complmented with behavior change interventions targeting drinking water treatment, handwashing and improved hygiene practices. Hence, we hypothesize that a combination of infrastructure and behavior related WASH interventions can influence children's health status. Children's health will further be influenced by the prevailing socio-demographic, socio-cultural, public policy and economic factors, and by the local food security situation.

[figure not shown]

Figure 1: Conceptual Framework of the Study

Assessment indicators

The indicators collected at the household level at the baseline and after the intervention will focus on:

- Water quality at point of collection
- Water quality at the point of consumption,
- Water safety plan management
- Availability, condition and use of WASH infrastructure
- Knowledge, attitude and practice of improved water management and hygiene
- Psychological factors
- Health indicators such as diarrhea and intestinal parasitic infections, particularly the count
 of intestinal helminthic and protozoan eggs. With regard to children's nutritional status, the
 hemoglobin level will be measured for anemia detection; stunting, wasting, thinness, mid
 upper arm circumference will be measured. Clinical examination for detecting wasted
 appearance, dermatitis, pale conjunctiva, xeropthalmia, night blindness, loss of hair
 pigments etc. will be assessed.

Study area

The study will be conducted in Kalikot, Jajarkot, Dailekh, Surkhet and Achham Districts in Western Nepal.

Study Procedure

[figure not shown]

Fig 2: Research Plan

Intervention package

Baseline data collection will take place in the study areas, where households have access to a piped water supply scheme but have not yet received the comprehensive WARM-P WASH intervention.

Data will be collected from 1500 households (375 households per area). Only households providing informed consent will be involved in the study. Intervention activities will start after the completion of baseline data collection in May 2018.

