3.3 Study procedures

Methods and approaches for objective 1: Water quality at the point of collection as well as at the point of consumption will be analyzed by field based methods using membrane filtration and the quantification of fecal indicators organisms such as E.coli and total coliforms. Water quality measurements will also include detection of free residual chlorine levels, turbidity, pH, conductivity, and nitrate.

Household information on WASH infrastructure, knowledge, attitude and practices will be gathered by a combination of qualitative (structured observations) and quantitative methods involving structured household interviews using tablets with digital questionnaires. Household survey questionnaires will include specific questions assessing KAP of WASH and health including household information, access to water, WASH know how, practice, attitude, self-efficacy, planning, behaviors, health status and risk awareness, social norms, perception of the water system, information on WASH promotion, market information, wealth index, and observation through interviewers.

Methods and approaches for objective 2: To determine the burden of water-borne diseases and the health impact of the interventions, the following indicators will be assessed by a combination of qualitative and quantitative methods:

- Diarrhea: baseline diarrhea incidence will be assessed by asking households about diarrhea
 prevalence during past 2 weeks prior to data collection. Households participating in the study
 will be requested to fill out a diary on diarrhea prevalence between baseline and of follow-up
 assessment.
- Intestinal parasitic infections: stool analysis will be done for determining the prevalence and type of intestinal parasites. Kato-Katz, formal-ether and wet mount methods will be used for soil-transmitted helminthes and intestinal protozoa respectively.

- Nutritional status: Anthropometric measurements for age will be used to account for normal growth and development of children. Children with z-scores for weight-for-height, weight-forage, and height-for-age <2 standard deviations of the median of the WHO reference population will be considered wasted, underweight and stunted respectively.
- Nutritional deficiency: Physical examination and clinical observation including dermatosis, pale conjunctiva etc. will be conducted by a trained health care professional. (food security will be assessed through questions in the interview)

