4 STATISTICS AND METHODOLOGY

4.1. Statistical analysis plan

Descriptive statistics will be calculated to describe the characteristics of the population and the status of WASH indicators. Frequencies and percentage will be computed for categorical variables while means and standard deviations will be calculated for continuous variables. Positive cases identified during health screening will allow estimating point prevalence. Pearson's chi squared and Fisher's exact test will be applied for finding the association with the prevalence of diarrhea, intestinal parasites (single, multiple), nutritional disorders and risk factors. Means will be compared by student's t test or ANOVA. Repeated measures multiple regressions will be used to find an association between binary or continuous outcomes and adjacent variables. Logistic regression analysis will be used to compare repeated binary health outcomes per child in multiple groups. Univariate association between two binary variables will be assessed through 2X2 tables. Categorical variables will be compared using design based chi-square analysis. In all analyses, a p- value (threshold of significance) <0.05 will be considered statistically significant.

Sample size and power calculations using G*Power 3.1 revealed a sample size of 350 households in each group to detect a small effect between 4 groups with a correlation of 0.1 among repeated measures with 80% power and a one-tailed alpha of 0.05 (Erdfelder *et al.* 1996). A sample size of 300 households will be required to detect a small to medium effect in Cohen's f2 at one-tailed alpha of 0.05 and a statistical power of 95% with multiple linear regression and 15 predictor variables (Faul et al., 2009).

We will sample 375 households per study area, which will have the advantage to better balance potential design effects. The same sampling plan will be used during the follow up study in both beneficiary and control areas. In addition, a drop-out rate of 7% is being considered.

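### No primary endpoint or contrast is named in section 2.2, while section 4.1 applies p<0.05 to every analysis, so a claimed health impact has no success criterion and no controlled error rate

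*Protocol*

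**What the plan says.** Protocol section 2.2 carries the heading "2.2 Primary and secondary endpoints". Its first objective covers water quality, infrastructure, and knowledge and practice. Its second covers child health: "To determine the burden of water-borne diseases (diarrhea and intestinal parasitic infections), malnutrition, nutritional deficiency and anemia among children". That makes five health constructs, listed as equals. Neither the word primary nor the word secondary is attached to any of them.

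Section 2.1, headed as hypothesis and primary objective, expects that the interventions "will lead to a reduction of the water-borne diseases including intestinal parasitic infections". This is a family of diseases, not one endpoint. The Goal in the same section also sets system-level chlorination against household water treatment, which is Area A against Area B.

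Section 3.3 divides the constructs further. Children below the z-score cut-offs "will be considered wasted, underweight and stunted respectively", which gives three anthropometric outcomes alongside diarrhoea, parasites, clinical deficiency and anaemia. The indicator list in 2.3 adds egg counts, thinness, arm circumference and several clinical signs. Section 6.3 adds a hypothesis that children under 5 benefit most.

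Section 4.1, the protocol's own statistical analysis section, states: "In all analyses, a p- value (threshold of significance) <0.05 will be considered statistically significant". It gives no hierarchy, primary contrast or adjustment. Its sample size is for a small effect between four groups and is tied to no named outcome.

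**The concern.** A confirmatory trial needs one stated result that would count as success, and a known probability of reaching it by chance. Here the section meant to supply the first does not, and the rule meant to govern the second is a per-test threshold applied to everything. With three active areas, one control area and several health outcomes, any favourable outcome-by-area result could be presented afterwards as the health impact, and a reader could not tell how many other results it was picked from. Section 2.3 calls the study a randomized controlled trial, and section 1 expects the findings to inform national policy and replication elsewhere, so the error rate of the headline claim matters.

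**Working it through.** The plan states no family-wise error rate, so there is no figure of its own to reproduce. The check asks how often at least one test falls below 0.05 when no intervention has any effect.

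**Inputs**
- Threshold per test: 0.05, unadjusted (section 4.1). The simulations use two-sided tests; 4.1 gives no sidedness for the analyses.
- Groups: four (section 2.3), hence three comparisons with Area D or six pairwise comparisons.
- Outcomes: five constructs (section 2.2), or seven when section 3.3 is counted out: diarrhoea, parasites, wasted, underweight, stunted, clinical deficiency, anaemia.
- Correlation between outcomes: not given in the protocol. Assumed, and varied from 0 to 0.8.
- Households treated as independent, because the protocol gives no intracluster correlation.

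**One four-group test per outcome, independent outcomes**
- Formula: 1 − (1 − 0.05)^k for k tests.
- Five constructs: 1 − 0.95^5 = 0.226, about 23%.
- Seven outcomes: 1 − 0.95^7 = 0.302, about 30%.

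**One outcome, several comparisons (simulated)**
- Three comparisons with D: 0.125.
- All six pairwise comparisons: 0.204.

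**Several outcomes, three comparisons with D each**

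The simple formula for 21 tests gives 1 − 0.95^21 = 0.659. That is too high, because the three comparisons share one control group and so are correlated. Taking 0.125 per outcome for seven independent outcomes gives 1 − (1 − 0.125)^7 = 1 − 0.393 = 0.607, which agrees with the simulated 61%.

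Simulated chance of at least one p<0.05:

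| Tests run | Corr. 0 | 0.3 | 0.5 | 0.8 |
|---|---|---|---|---|
| 5 outcomes, one four-group test each | 23% | 21% | 19% | not run |
| 7 outcomes, one four-group test each | 30% | 28% | 24% | not run |
| 5 outcomes × three versus D | 49% | 46% | 41% | 30% |
| 7 outcomes × three versus D | 61% | 56% | 49% | 34% |

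Every entry is well above 5%. A single named endpoint with a single test at 0.05 would have a 5% error rate by construction.

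**The case against.** **The statistical analysis plan may settle this.** Multiplicity adjustment is often left to a SAP, and one may exist that is not shown. That would be a good answer if the protocol were silent. But section 2.2 is headed for the purpose and leaves it undone, and 4.1 fixes its threshold for all analyses. A SAP that adjusted for multiplicity would contradict that sentence. The unnamed primary is the firmer half of the point.

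**A false positive is not necessarily likely.** A reader might infer that chance alone will probably produce a significant health effect. The protocol does not support this, because it fixes no number of tests. Section 4.1 mentions ANOVA and logistic regression across multiple groups; one such test per outcome gives 23% or 30%. Among the cases tabulated, only seven outcomes with three comparisons each exceeds 50%, and then only at low to moderate correlation. The outcomes are plainly related: wasted, underweight and stunted come from the same measurements, and pale conjunctiva overlaps with anaemia. The count of seven is itself a reading of 3.3, where clinical deficiency has no binary definition.

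**There is an implied order.** Section 2.1 aims at water-borne diseases, which 2.2 explains as diarrhoea and intestinal parasites, and the conceptual framework in 2.3 places nutrition downstream. This narrows the family but does not close it. Two outcomes with one test each give 1 − 0.95^2 = 0.0975, about 10%. With three comparisons with D each, simulation gives 23.5% at zero correlation and 18.9% at 0.8.

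**Section 4.1 states a conventional per-test threshold.** It does not say that any single p<0.05 would establish the health impact, and a reader should not take it to say so. What stands is that nothing in the protocol says what would establish it.

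**Conclusion.** The point holds. Section 2.2 names no primary endpoint or contrast, 2.1 gives a disease family, the sample size in 4.1 is tied to no outcome, and 4.1 applies an unadjusted 0.05 throughout. A health-impact claim therefore has neither a defined success criterion nor a controlled error rate.

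Under no effect, the chance of at least one p<0.05 is about 23% for the five constructs and 30% for seven outcomes (one four-group test each, independent outcomes). For seven outcomes compared three times with Area D it is about 34% to 61%, at outcome correlations from 0.8 down to 0. The size depends on how many tests are run and on assumed correlations, so it should be quoted as a range. All figures treat households as independent. The interventions are delivered by area or water scheme, and positive correlation within areas, if ignored, would raise the error of each test further.

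**What to change.** Before follow-up data are seen, amend the protocol as follows.

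- **Section 2.2, endpoint.** Name one primary health endpoint from the water-borne diseases in the 2.1 hypothesis: diarrhoea or any intestinal parasitic infection. Laboratory-confirmed infection is one defensible choice. Diarrhoea is also supported, since 3.1 and 6.3 build their rationale on it. Two points bear on the choice. Infected children are treated after testing, which affects what infection at follow-up measures. Diarrhoea is collected both by two-week recall and by diary, so the measure used would have to be stated.
- **Section 2.2, contrasts.** Name A, B and C each versus D, plus A versus B because the Goal in 2.1 states that comparison.
- **Section 4.1, testing.** Test these four contrasts with Holm at overall 0.05, so that the smallest p-value is judged against 0.05/4 = 0.0125. Use an analysis that respects delivery by area or scheme; Holm applied to household-level tests would not by itself secure the overall 0.05.
- **Other outcomes.** Label them secondary or exploratory and report them with confidence intervals. Limit the sentence in 4.1 about all analyses accordingly.
- **Sample size.** Restate the power, or the detectable effect, of the planned 375 households per area for the chosen endpoint and contrasts.

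The cost is lower power per contrast, fewer outcomes open to a significance claim, a restated sample-size justification, and an amendment by the route in section 5.5. No new data are needed.
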